9.2.2. Medical History

Medical history will be obtained at Screening and should include demographic information (date of birth, race, ethnicity) and subject's medical and surgical history. The medical history must be documented in the subject's eCRF.

9.2.3. Clinical Laboratory Evaluations

Blood samples will be collected and documented by the Investigator (or designee) for clinical laboratory evaluations (including clinical chemistry, hematology, and coagulation tests) at the times indicated in the Schedule of Assessments in Appendix 4. Clinical laboratory evaluations are listed in Appendix 2. **Of note:** if multiple sets of labs are obtained for a subject within the same post-operative day (either as part of standard institutional protocols, or due to changes in the subject's clinical picture), the lab assessments obtained at the time which *most closely approximates* 24hrs, 48hrs, 72hrs, etc., post-op should be the values entered into the EDC for study purposes.

Instructions for the collection and storage of study samples that will be analyzed by the Central Laboratory are provided in the Study Laboratory Manual.

9.2.4. Vital Signs

Supine blood pressure, pulse rate, respiratory rate, oxygen saturation, and body temperature will be assessed at the times indicated in the Schedule of Assessments in Appendix 4. Vital signs may also be performed at other times if judged to be clinically appropriate, or if the ongoing review of the data suggests a more detailed assessment of vital signs is required.

All measurements will be performed singly and repeated once if outside the relevant clinical reference range.

9.2.5. Physical Examination

Body mass index will be calculated using the subject's body weight and height at the time of screening (Schedule of Assessments, Appendix 4). A physical exam (PE) will be performed and documented at the time of screening/subject enrollment. Physical exams performed as part of standard of care on the day of screening but occurring prior to signing of informed consent may be documented as the screening PE. A physical exam will be repeated on the day of the procedure, if the day of the procedure is different than the day of screening.

9.2.6. Other Assessments: Blood Products and Blood Loss

Intraoperative and postoperative blood loss and chest drainage volumes (chest drainage includes output from all chest and mediastinal tubes) will be measured and documented at the times indicated in the Schedule of Assessments in Appendix 4. Cellsaver will **not** be included in the calculation of blood product transfusions, as this is volume that would normally be given back as part of standard of care. Chest tube drainage will be recorded in the corresponding *Chest Tube Drainage eCRF* for at least 24hrs post-operation, unless unable to do so (i.e., subject death prior to 24hrs). Volume of blood loss not coming from chest/mediastinal drainage will be documented separately, in the corresponding *Blood Loss (Non-Chest Drainage) eCRF*. Blood products received by the subject will be recorded in the corresponding *Transfusion eCRF*.

9.3. Blood Sampling for Drug Removal

Blood samples for the analysis of plasma ticagrelor concentrations will be collected at the times indicated in the Schedule of Assessments in Appendix 4 and will be stored until analysis. A pre-CPB sample will be obtained prior to the start of cardiopulmonary bypass, and up to 2hrs pre-start of surgery (i.e., time of skin incision). While the subject is on CPB, serial samples will be drawn at 30 ± 15 min following initiation of CPB, at 60min, at 90min, and at 120min of CPB time. A post-CPB sample will be obtained as soon as possible following the end of CPB, and no later than 30min after the subject has been disconnected from the CPB circuit.

If the total CPB time required for the procedure is <120min (2hrs), the serial sampling will only be

performed through the required duration of CPB. For procedures requiring >120min (2hrs) of CPB time, serial sampling will **not** extend beyond this time point, as the incremental change is expected to be minimal compared to the post-CPB value. Processing, storage, and shipping instructions for these blood samples will be provided by the Sponsor (or designee) to the investigation sites, and detailed in the Study Laboratory Manual. Samples will be stored and analyzed at a designated bioanalytical laboratory using a validated assay. Any residual samples will be destroyed at the completion of the final investigation report or if the subject withdraws assent/consent to use the sample for the research purposes of the investigation.

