The primary effectiveness endpoint will be evaluated using the Win Ratio method of analysis for a hierarchical composite endpoint based on the Finkelstein-Schoenfeld test (Finkelstein and Schoenfeld, 1999; Pocock, et al., 2012) with three components: a) fatal perioperative bleeding events (within 48hrs of the index procedure), b) moderate, severe, or massive bleeding based on the Universal Definition of Perioperative Bleeding in Cardiac Surgery (UDPB) ≥ 2 classification, and c) 24-hour chest tube drainage (volume, mL). The Win Ratio assigns “wins”, “losses”, or “ties” between randomized groups in a serial fashion across all components of the composite endpoint adhering to the declared hierarchical order from higher to lower clinical importance.[9] [10] A ratio of “wins” greater than 1.0 favors the treatment arm; when the lower bound of a 95% confidence interval (CI) around the ratio exceeds 1.0, the treatment is shown to be statistically superior to control at alpha = 0.05.

The key secondary effectiveness endpoint is the pre-CPB vs. post-CPB change in ticagrelor blood levels as measured by liquid chromatography/tandem mass spectrometry [drug removal endpoint]. Change in each subject's blood concentration of ticagrelor (Δ [ticagrelor]) from immediately before to immediately after CPB will be collected and analyzed by a central core laboratory.

Change from baseline in blood concentration of ticagrelor is defined as:

$$\frac{\text{pre-CPB } [\text{ticagrelor}]_{\text{blood}} - \text{post-CPB } [\text{ticagrelor}]_{\text{blood}}}{\text{pre-CPB } [\text{ticagrelor}]_{\text{blood}}} * 100\%$$

Based on existing benchtop evidence, a conservative estimate of 40% reduction in blood concentration of ticagrelor between pre- and post- DrugSorb™-ATR removal is expected, with a standard deviation of 40%, in the treatment arm. Minimal change is expected in the control arm. A two-sample t-test will be used to evaluate the difference between treatment arms. We anticipate that drug removal data from clinical use in this application will become available during the course of the study and we plan to validate the above assumption based on the *in vivo* data.

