1.5. Study Design

The STAR-T study is designed to demonstrate reductions in postoperative bleeding complications with the intraoperative use of DrugSorb™-ATR in patients undergoing cardiothoracic surgery within two days of ticagrelor discontinuation. These patients have been demonstrated in the literature to be at

greatest risk for bleeding complications (refer to **Section 3** for details). The study also aims to establish the safety of intraoperative DrugSorb™-ATR use in the target population.

The mechanism of action is removal of ticagrelor from active circulation through hemoadsorption while the patient is on cardiopulmonary bypass. Thus, the change in total blood concentration of ticagrelor following CPB will be measured as a key secondary endpoint. To do so, patient blood samples will be obtained during the pre-operative and immediate post-CPB time periods for ticagrelor concentration testing. This will allow comparison of clinical outcomes with presence or absence of reduction in circulating drug concentration. Serial sampling (every 30 min) for quantification of serial changes in blood ticagrelor levels will also be obtained through the first 2 hours of therapy on CPB. This supplemental drug removal data will be analyzed as an exploratory endpoint. Additional outcome measures to be evaluated include those that are documented as part of routine care, and are detailed in **Section 4.3**.

[figure not shown]

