9.1. Procedures and Assessments by Study Phase

Subjects are considered enrolled in the study at the time which consent or assent (in the case of a proxy providing permission for an incapacitated subject) to participate in the study is provided. Details on the consent process are provided in **Section 4.4.3** and the ethics of consenting non-vulnerable and vulnerable (incapacitated) populations are detailed in Appendix 3.

Subjects who do not meet study entry (inclusion/exclusion) criteria are screening failures and will exit the study. Treated subjects will be followed up through 30 days after the surgical procedure.

The start of the investigation is defined as the date of consent to enroll the first prospective subject. The end of the investigation is defined as the date of the last subject's last contact or assessment (whether scheduled or unscheduled).

[figure not shown]
The investigation is divided operationally into 6 phases:

- Screening Phase – the period between the time consent/assent is provided for study

participation and the start of the surgical procedure with CPB

- **Pre-CPB Phase** – the period within 2 hours of start of the operation with CPB (time of skin incision). *Note: The Pre-CPB Phase may overlap with the Screening phase.*
- **Operation Phase** – the start of the surgical procedure (defined as skin incision) until chest closure.
- **Post-CPB Phase** – the period from the end of CPB up to admission to the Intensive Care Unit (ICU). *Blood sampling for drug removal obtained in the post-CPB phase should be drawn as soon as possible following the end of CPB, and no later than 30 min after the subject has been disconnected from the CPB circuit.*
- **Post-operation Phase** – from admission to the ICU through Day 29 or the point of discharge from hospitalization, whichever is sooner. **Discharge from hospitalization** means the date of initial discharge from the hospital in which the cardiothoracic surgery was completed (i.e., index procedure) irrespective of discharge to home care, secondary care or other rehabilitation unit.
- **Day 30 Evaluation Post-Cardiothoracic Surgery** – The subject status on postoperative day 30 will be evaluated by telephone contact, in-person follow-up visit, or review of medical records. Assessment of mortality (i.e., vitals status), blood product transfusions, and other adverse events will be performed.

An overview of the investigation design is shown in **Figure 5**.

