9.1.2. Operation Phase

The Operation Phase will be initiated at the time of first incision. During the Operation Phase, the subject will either undergo standard CPB, or CPB + DrugSorb™-ATR according to randomization.

Subjects randomized to the control arm will receive standard of care in which a sham device will be in place parallel to the CPB circuit, but through which no blood will circulate. Refer to **Section 6.3** for details.

In the treatment arm, DrugSorb™-ATR treatment will initiate with the start of CPB and continue through the end of CPB. Per the Instructions for Use (IFU) and under the guidance of a Field Clinical Engineer, the DrugSorb™-ATR device will be placed into a parallel bypass circuit to the main blood flow in a standard heart-lung machine circuit and primed for use in preparation for the Operation Phase. Throughout the treatment session, the DrugSorb™-ATR device will be monitored for blood leaks, flow changes, and/or clots. Any adverse device events and/or device observations must be recorded by indicating the location of leaks and/or by recording the size of any clots present.

DrugSorb™-ATR treatment flow rates will be controlled utilizing a roller clamp placed on the distal, superior line above the DrugSorb™-ATR prior to returning to the reservoir. Flow rate will be measured using a Sponsor provided Transonic (or equivalent) ultrasonic flow meter and probe, also on the inlet line below the DrugSorb™-ATR device. **The blood flow rate of the device will be adjusted to 500mL/min ±100mL/min (minimum above 400mL/min is acceptable).**

During the operation phase, arterial blood gas analysis will be obtained at the following time periods: within 30min pre-CPB, 30 ±15min into CPB, within 30min post-CPB, and upon admission to the ICU. Activated clotting time will be obtained once at 30 ±15min into CPB, and once within 30min post-protamine administration. All other assessments including monitoring of transfusions, will be performed as detailed in **Table 6** of Appendix 4. Intraoperative transfusions will be administered at the discretion of the investigator in accordance with standard practices but should follow Best Clinical

Practice Guidelines.

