Benchtop studies of drug removal by the DrugSorb™-ATR device (CytoSorbents, unpublished data) demonstrate concentration and time dependent absolute drug removal. Based on these benchtop studies, a conservative estimate of 40% reduction in blood concentration of ticagrelor between pre- and post- DrugSorb™-ATR removal is expected, with a standard deviation of 40%, in the treatment arm. Minimal change is expected in the control arm. A two-sample t-test will be used to evaluate the difference between treatment arms. Due to highly variable baseline ticagrelor blood levels in the above benchtop studies, percent change from baseline will be analyzed as opposed to observed values. We anticipate drug removal data from other clinical studies in this application to become available during the course of the study and we plan to update the above assumption if necessary based on *in vivo* data.

Additional powered secondary endpoints include 24-hour CTD (volume [mL]), total platelet transfusions during the index hospitalization (volume [mL] and units), and total PRBC transfusions during the index hospitalization (volume [mL] and units). Twenty-four-hour CTD (mL) will be assessed via two-sample t-test for mean difference. In the event the assumptions for a two-sample t-test are not met, a nonparametric test such as a Mann-Whitney test will be employed, with median and range values provided in the output. The transfusion endpoints will all be analyzed using two-sample t-tests for mean differences, and Fisher-Freeman-Halton exact tests for units. In the event the assumptions for a two-sample t-test are not met, a nonparametric test such as a Mann-Whitney test will be employed, with median and range values provided in the output. Other secondary endpoints include the remaining Win Ratio component parts: proportions of fatal perioperative bleeding events will be assessed via Fisher’s exact test; and proportions of UDPB events (by category) will be

assessed via a Fisher-Freeman-Halton exact test. All surgical re-exploration for excessive bleeding, including those events occurring beyond the timeframe captured within the UDPB component of the primary endpoint will be captured as a secondary endpoint. Time to re-exploration will be taken into account.

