### 1.3.7. Exploratory Subgroup Analyses

The primary effectiveness endpoint and its individual components will be analyzed in the following subgroups:

1. Surgical Characteristics
  - a. Procedure duration (skin incision to closure): <4 hours vs. 4-6 hours vs. >6 hours
  - b. CPB duration (i.e., device exposure):
    - Tertiles
    - Above and below median
2. Drug Removal
  - a. Time from Last Dose:
    1. Tertiles
    2. 0-24 vs. 24-48 vs. >48 hours
    3. above vs below median
    4. 0-24 vs. >24 hours
    5. 0-48 vs. >48 hours
  - b. Ticagrelor Levels
    6. Above vs. Below median pre-CPB levels (whole population)
    7. Above vs. Below median post-CPB levels (whole population)
    8. >67% vs. <67% removal (per intervention arm values)
    9. >50 vs. <50% removal (per intervention arm values)
    10. >40 vs. <40% removal (per intervention arm values)

The key secondary endpoint will be analyzed according to surgical characteristics and the time from last dose subgroups.

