### A 1.1 Pharmacokinetic Assessment

#### A 1.1.1 Sample Collections for Pharmacokinetic Analysis

PK Blood samples will be collected for the determination of plasma ticagrelor and desethoxyhydroxy ticagrelor (ticagrelor active metabolite, TAM) concentration. The pre-CPB blood sample will be drawn prior to the start of CPB and can be up to 2hrs prior to skin incision. During the procedure, while the subject is on CPB, serial samples will be drawn at  $30\pm15$ min following initiation of CPB, at 60min, at 90min, and at 120min of CPB time. If the total CPB time required for the procedure is  $<120$ min (2hrs), the serial sampling will only be performed through the required duration of CPB. A post-CPB sample will be obtained as soon as possible following the end of CPB, and no later than 30min after the subject has been disconnected from the CPB circuit. The actual date and time of collection of each PK sample will be recorded.

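### The pre-CPB ticagrelor sample may be drawn up to 2 h before skin incision, so change before the device runs enters percent removal in both arms and blurs the size of the key secondary endpoint

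*Protocol*

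**What the plan says.** The Synopsis (Statistical methods) describes the key secondary as each subject's change in ticagrelor concentration "from immediately before to immediately after CPB will be collected and analyzed by a central core laboratory". The other endpoint definitions (Protocol 4.3.2 and 11.3, SAP 1.3.2) say only pre-CPB versus post-CPB.

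The sampling instructions are wider than the Synopsis. Protocol 9.3: "A pre-CPB sample will be obtained prior to the start of cardiopulmonary bypass, and up to 2hrs pre-start of surgery". SAP A 1.1.1: "The pre-CPB blood sample will be drawn prior to the start of CPB and can be up to 2hrs prior to skin incision". Table 6 footnote d says the same, and the Pre-CPB column of Table 6 and the phase definition in Protocol 9.1 are both tied to skin incision, not to the start of CPB. Protocol 1.5 says that "patient blood samples will be obtained during the pre-operative and immediate post-CPB time periods for ticagrelor concentration testing". The post-CPB sample, by contrast, must be drawn within 30 min of disconnection (Protocol 9.3).

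The endpoint is the fall in concentration divided by the pre-CPB value. Protocol 11.3 assumes a 40% reduction with SD 40% in the device arm, and for control: "Minimal change is expected in the control arm". SAP 5.3.1 compares raw percent change with an unadjusted two-sample t-test. SAP A 1.1.1 records actual sampling times, but the key secondary analysis does not use them.

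**The concern.** The two ends of the interval are not held to the same standard. A site that follows the Pre-CPB column of Table 6 draws the baseline before incision, possibly hours before the device carries any blood. The protocol itself recognises natural washout (sections 3 and 4.1), so concentration is not constant over that gap. Because the pre-CPB value is the denominator, a fall during the gap is counted as removal in both arms, and the arm difference is scaled down by the fraction already lost.

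The second study objective is to show a reduction in ticagrelor with intraoperative use of the device. What is at stake is how large that reduction appears to be, whether the control-arm assumption is credible, and what the exploratory removal subgroups at 40, 50 and 67% (SAP 1.3.7) mean. Lead time may also vary by site and urgency, which adds noise.

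**Working it through.** **The plan's own figure.** Difference 40 points, SD 40, 57 per arm, two-sided alpha 0.05, equal variances: the noncentral t gives 99.96% power. The stated >99.9% is reproduced.

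**Assumptions not in the documents.** First-order washout; half-life 6-12 h; lead (sample to CPB start) 3 h, for example 2 h before incision plus 1 h to CPB, compared with 0.5 h; 2 h from CPB start to the post-CPB sample. The device removes r = 0.40 of the drug present, the plan's figure.

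**Formulas.** Fraction left when the device starts: f = 2^(-lead/half-life). Fraction left after natural washout on CPB: c = 2^(-2/half-life).

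- Control change = 1 - f·c
- Device-arm change = 1 - (1 - r)·f·c
- Arm difference = r·f·c

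Setting c = 1 isolates the effect of the sampling window.

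**Lost before the device starts (1 - f).** Lead 3 h: 1 - 0.707 = 29% (6 h half-life) and 1 - 0.841 = 16% (12 h). Lead 0.5 h: 1 - 0.944 = 6% and 1 - 0.972 = 3%.

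**With the same 2 h of on-CPB washout in every row** (c = 0.794 for 6 h, 0.891 for 12 h):

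| Lead | Half-life | f·c | Control change | Device-arm change | Difference |
|---|---|---|---|---|---|
| 3 h | 6 h | 0.561 | 43.9% | 66.3% | 22.4 |
| 0.5 h | 6 h | 0.749 | 25.1% | 55.1% | 30.0 |
| 3 h | 12 h | 0.749 | 25.1% | 55.1% | 30.0 |
| 0.5 h | 12 h | 0.865 | 13.4% | 48.1% | 34.6 |

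The share due to the window is 30.0 - 22.4 = 7.6 points (6 h) and 34.6 - 30.0 = 4.6 points (12 h), so about 5-8 points.

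**Power with lead-time washout only (c = 1), SD 40, 57 per arm.** Lead 3 h: differences 28.3 and 33.6 points (half-lives 6 and 12 h), power 96.3% and 99.4%. The worst case examined, a 4 h lead with a 6 h half-life: 25.2 points, power 91.5% (94.6% at 65 per arm). Leads spread evenly over 0.5-4 h add 5-9 points of SD and leave power at about 98% or more.

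**Removal cut-offs, lead-time washout only.** A subject with 40% true removal reads above 50% once 0.6·f < 0.5, that is f < 0.833. This needs a lead above 1.6 h (6 h half-life) or 3.2 h (12 h). To read 67% at a 3 h lead and 6 h half-life, true removal need only be 1 - 0.33/0.707 = 53%.

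**Why a log ratio helps.** In this model log(post/pre) = log f + log c, plus log(1 - r) in the device arm. The arm difference is log 0.6 = -0.51 whatever the lead, and lead enters additively. On the percent scale it multiplies the treatment effect, so an additive covariate there reduces noise but does not undo the attenuation.

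**The case against.** The strongest reply has several parts.

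- **The textual conflict is narrow.** Only the Synopsis requires sampling immediately before CPB; the operative sampling sections agree with one another. That stands: correcting one phrase would reconcile the text, but would leave the wide window and its effect on percent removal.
- **Much of the gap from 40 points is not due to the window.** A reader might infer that the whole 25-44% control change, and the fall from 40 to 22-30 points, comes from early sampling. It does not. With a 30-min sample the control change is still 13-25% and the difference 30-35 points, because washout also continues during CPB.
- **Inference survives.** A reader might infer an invalid test or inflated type I error. The documents do not support this: the same window applies to both randomised arms, so with no device effect both have the same expected change. Nor does the window by itself leave the endpoint underpowered. Power falls below 80% only when on-CPB washout is added to the worst lead (4 h lead, 6 h half-life, 1.75 h on CPB and after: 20.6 points, 77.8% at 57 per arm). The plan also calls 40% conservative; at 60% removal the 3 h rows give 34-45 points.
- **The direction is not fixed.** Surgery on the day of the last dose is eligible. If levels are still rising, f exceeds 1, removal is understated and the difference grows. This stands.
- **Other analyses help.** SAP A 1.1.4 compares concentrations at each time point, including post-CPB, without the pre-CPB denominator, and SAP 1.3.7 examines the key secondary by time from last dose. Neither adjusts the key secondary for sampling lead, and the removal cut-offs, though only exploratory, remain affected.

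**Conclusion.** The point holds as an inconsistency in the sampling window with a moderate effect on the estimate. The Synopsis and the sampling sections describe different intervals, and the wider one lets change before device exposure count as removal. Under first-order washout with a 6-12 h half-life and a 3 h lead, 16-29% of the drug is gone before the device starts, against 3-6% with a 30-min sample, and the window costs about 5-8 points of arm difference. These sizes rest on a half-life and lead time that the documents do not give; nothing shows how early sites actually sample, and in recently dosed subjects the sign could reverse.

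The significance test stays valid, and lead-time washout alone leaves power at about 91% or more at 57 per arm. The harm is to the size and interpretation of removal: the percentage reported in each arm, the assumption of little change in control, and the 40, 50 and 67% subgroups. It is worth fixing because the fix is cheap.

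**What to change.** 1. State one pre-CPB sampling window in the Synopsis, Protocol 9.3, Table 6 (Pre-CPB column and footnote d) and SAP A 1.1.1.
2. For future subjects, draw the ticagrelor sample with the blood gas that Protocol 9.1.2 already requires: "arterial blood gas analysis will be obtained at the following time periods: within 30min pre-CPB". No additional sampling occasion is needed.
3. For all subjects, add a sensitivity analysis of the key secondary that uses the recorded interval from sample to CPB start. Either fit percent change with a treatment-by-interval term, or fit the log ratio of post- to pre-CPB concentration with interval as a covariate. This also allows subjects sampled under the old and new windows to be combined.
4. Replace the control-arm assumption in the Synopsis and Protocol 11.3 with an explicit expected decline that also covers washout during CPB, since no change to the pre-CPB window removes that part.

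The cost is wording, laboratory-manual timing, one added analysis and probably a few more timing deviations. SAP section 2 refers to drainage variability already observed, so enrolment appears to be under way and tightening now would leave two baseline windows in one trial. The interval-adjusted analysis is there to handle that.
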